Our pre-specified inclusion criteria will minimize selection bias since infant appearance at birth, rather than actual cord management, determines which infants are included. Allocation bias will be prevented since all non-vigorous infants will receive the same treatment during the prescribed epoch. It is impossible to blind obstetrical providers or parents to the assigned treatment arm. To avoid clinical team bias we will request documentation of the specific intervention (UCM or ECC) not be included in the infant's medical record. Since cord management is not routinely provided in the medical record we have specifically avoided any inclusion of the management to avoid downstream bias once the study has begun. In order to prevent admission bias in either of the prescribed epochs, we have outlined pre-specified criteria that will constitute a NICU admission for purposes of this study, see appendix 2.

Specific Aim 2 (SECONDARY) Compare the safety and efficacy profiles of non-vigorous newborns 35-41+6 weeks GA delivered receiving UCM vs. ECC during their birth hospitalization and at 24 months corrected age.

H2: Compared to ECC subjects, UCM subjects will have higher cerebral oxygen saturations at 10 minutes of life (sub-study at three (3) sites, n=20).

Rationale: Caregivers and researchers raised theoretical concerns that the UCM technique may deliver blood rapidly toward a non-vigorous newborn predisposing them to higher rates of brain injury or dislodging cellular debris into the brain. However, of the 13 studies on term infants comparing UCM to ECC, none have reported adverse outcomes. All demonstrated improvements similar to DCC with increased red cell mass (measured by hematocrit or hemoglobin) improved blood pressure, increased pulmonary blood flow and improved ferritin at 6 weeks to 6 months of age with UCM. Nevertheless, careful assessment of safety is essential. Immediate physiological measurements on a subset (n=20) of infants of the three sub-study sites where the use of NIRS is standard of care, University of Alberta, SMBHWN and SGH to establish the safety and efficacy of UCM. This aim will further test our hypotheses that infants in the UCM group will have improved early cardiac and cerebral hemodynamics within the first 10 minutes.

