As with any study, there may be risks that currently are unforeseeable.

Risk Management

Protection against Risk

Practitioners at all sites have experience with performing UCM and ECC within their normal clinical care. Only research team members (with appropriate research training relevant to protection of human subjects) shall have access to the project's databases.

Management of Risks

Hemoglobin lab draw: Will be performed by clinical staff that are trained and experienced in drawing blood from newborns. Proper techniques will be used at all times to minimize the chance of infection thereby minimizing potential risks related to the collection of blood samples. All efforts will be made to reduce infants discomfort (i.e. warming infants heel, providing oral glucose, or hospital standard practice).

Data Collection and Survey Completion

All data will be safeguarded in accordance with the Health Insurance Portability and Accountability Act (HIPAA) and the principles and practices of strict confidentiality. Every reasonable effort will be made to keep the subjects records confidential. Subject's records will be stored in a secure office. Codes, instead of names, will be used to identify the collected information.

Reporting Process

The population being studied is at increased risk of all complications (such as hypoxic ischemic encephalopathy) associated with term and near-term infants who are deemed to require immediate resuscitation. The majority of these events will be expected and included in data collection and reported in all DSMB analyses. However, all SAE's of death, polycythemia/jaundice requiring exchange transfusion, pulmonary hemorrhage and severe IVH (grade 3 or 4) on HUS or MRI will be reported within 3 days of discovery of event, to UCSD DCoC via REDCap.

Monitoring

The DCoC will send out monthly reports detailing enrollment, SAE's, protocol deviations and data queries. Clinical Coordinating Center (SMBHWN) Data team will be monitoring sites as needed throughout the trial. The purposes of monitoring visits, which will generally be done by phone or GoToMeeting, are to:

- Ensure the rights and safety of participants
- Confirm that the study is conducted in accordance with GCP guidelines
- Ensure maintenance of required documents
- Verify adherence to the protocol
- Monitor the quality of data collected
- Ensure accurate reporting and documentation of all AEs and unanticipated problems

Data Safety Monitoring Board (DSMB)

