An expert board consisting of perinatologists, neonatologists, outside statisticians and a former NICU parent will be closely reviewing all serious adverse outcomes. This group has been established to: 1) protect all study patients, 2) safeguard the interests of all study patients, 3) monitor the overall conduct of the trial, 4) advise the investigators to protect the integrity of the trial, and 5) supervise the conduct and analysis of all interim analyses. The DSMB will review the first 200 enrolled infants. If the first review does not show any evidence of safety signal for adverse outcomes in either group on blinded analyses, additional blinded reviews will be conducted when 50 and 75 percent of subjects are enrolled. If the odds ratio of NICU admission or death between the two arms exceeds a threshold, it will trigger a safety signal. We will suggest to the DSMB the threshold of an odds ratio of 2.5 as the threshold for a formal meeting to discuss potentially stopping the trial. However, the DSMB should discuss and determine the threshold. There is no plan to stop for efficacy as the trial design (cluster randomized cross-over) necessitates that both arms of the trial be completed at each site before efficacy can be

adequately assessed. If the trial were stopped prematurely, we would perform planned analyses on the data collected at the time of the closing of the study. The findings will be communicated to all study staff by the data center in monthly reports via email. According to the study's Statistical Analysis Plan and due to the cross-over design of the study, there will be no planned formal interim analysis for efficacy or futility.

IX. Data Management

Centralized Data Collection

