Notification of Parents prior to enrollment: Both mother and baby will be subjects in this study. We are informing parents in three ways. First, all obstetric practices that refer babies to the study hospitals will have information such as brochures in their offices, at prenatal childbirth education classes and the obstetrician will discuss hospital's participation in the study with their patients. Second, there will be signs (to be developed from handout) about the study at prenatal sites and physician offices. Both will have information for parents about contact information of the researchers. Finally, there will be information about the study on the Sharp website with answers to frequently asked questions. High visibility posters of the study and information brochures will be posted in the hospitals for limited to no prenatal care situations and for those that may not have access to internet resources. All documents created for parent notification will be submitted for IRB approval before use.

Protocol Deviations

The following deviations will be entered on the Deviation Report Form in REDCap as they are identified:

- Cord clamping ≥ 60 seconds will be considered a protocol violation and analyzed due to the confounding effects of delayed cord clamping.
- Patient did not receive correct treatment arm.

Serious Adverse Events (SAE)

All SAE's of death, polycythemia/jaundice requiring exchange transfusion, pulmonary hemorrhage or severe IVH (grade 3 or 4) on HUS or MRI will be reported within 3 days of discovery of event, to UCSD DCoC via REDCap. The DCoC will forward all SAE reports to the DSMB and PI.

Unanticipated Event or Problems

The investigator will be responsible for reporting an unanticipated adverse event in REDCap, if it meets all of the criteria listed below:

1. It is an unexpected event (nature, severity or frequency) and not addressed within the study protocol or informed consent document
2. It is related or possibly related to the research as determined by the PI – there is a reasonable possibility that the event may have been caused by the procedures involved in the research
3. And suggests that the research places the subject or others at a greater risk of harm than was previously known or recognized (including physical, psychological, economic, or social harm)

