If the unanticipated event is determined serious by the PI, it must be reported to the DCoC within three (3) days in REDCap; within 14 days for a Non-serious unanticipated event. The DCoC will report this to the DSMB who will determine if the adverse event changes the known risk to study subjects. If the information changes the known risk to subjects, the DSMB's report regarding the change in risk will be released to all participating investigators. The DSMB may request changes to the DSMP.

Data Safety Monitoring Board (DSMB)

A DSMB has been established to:

- 1) Protect all study patients
- 2) Safeguard the interests of all study patients
- 3) Monitor the overall conduct of the trial
- 4) Advise the investigators to protect the integrity of the trial, and
- 5) Supervise the conduct and analysis of all interim analyses.

The DSMB will receive regular reports from the trial on any injuries or adverse events, any developments that jeopardize the continued success of the trial, and data by which to accomplish the evaluation of pre-determined early stopping rules. All Serious Adverse Events (**SAEs**) will be reported within 3 days of discovery to the Data Coordinating Center (**DCoC**) and forwarded to the DSMB; reports of adverse events and recruitment will be sent monthly; demographics will be included with the interim and final safety and efficacy analyses. The DSMB will conduct interim analyses and project statisticians, independently from the trial leadership and staff. The role of the trial investigators is to notify the IRB of any issues that are relative to patient safety or to early stopping of the study. The study will be closely monitored for issues of data quality, study conduct, and adverse events. These analyses will be presented to the DSMB.

Trial Timeframe

Trial stages	Timeframe
Protocol development	April- June 2018
Protocol finalized	July 2018
Site determination	June 2018, Investigator Meeting
Sites submit IRB application	July-August 2018
Finalize contracts and payment methods	September-October 2018
Site Randomization and education	October – December 2018
Recruitment phase	January 2019- March 2021
Assessment phase	Primary outcome June 2021
Analysis	2021 for primary outcome, 2023 for neurodevelopmental outcomes
Publication	2021 on primary outcome, 2023 for neurodevelopmental follow-up

Publication Plan

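### The plan mails findings to all study staff every month, which conflicts with its own provisions on interim analyses and DSMB reports, and it does not limit what monthly safety reports show

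*Combined protocol and SAP*

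**What the plan says.** The relevant places in the combined protocol and SAP are these.

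- **Section VIII, Data Safety Monitoring Board (DSMB).** The board looks at the first 200 infants. If there is no safety signal, "additional blinded reviews will be conducted when 50 and 75 percent of subjects are enrolled". The signal compares the arms: "If the odds ratio of NICU admission or death between the two arms exceeds a threshold, it will trigger a safety signal". The suggested threshold is an odds ratio of 2.5. The paragraph then covers early closure ("If the trial were stopped prematurely, we would perform planned analyses on the data collected at the time of the closing of the study"), and the next sentence is "The findings will be communicated to all study staff by the data center in monthly reports via email". It ends by ruling out a formal interim analysis of efficacy or futility.
- **Section VIII, Monitoring.** "The DCoC will send out monthly reports detailing enrollment, SAE's, protocol deviations and data queries". No recipient is named, and nothing says whether figures are pooled or shown by site or arm.
- **Section IX, Serious Adverse Events (SAE).** "The DCoC will forward all SAE reports to the DSMB and PI".
- **Section IX, Data Safety Monitoring Board (DSMB).** Interim analyses are conducted "independently from the trial leadership and staff".
- **Section IX, Unanticipated Event or Problems.** A DSMB report goes to participating investigators if the information alters the known risk.
- **Section III, Preparation of sites for the trial; Section IV, Prevention of Bias in an unblinded trial.** Each site is told its allocation before it starts, and "It is impossible to blind obstetrical providers or parents to the assigned treatment arm".

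**The concern.** NICU admission is the primary endpoint and also part of the quantity the DSMB reviews. Taken at face value, Section VIII sends the outcome of those reviews to everyone working on the study while enrolment continues.

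In this design, coded arm labels give little protection. A hospital delivers one openly known treatment for up to a year, so a safety table by site and month is a table by arm for any reader who knows the allocation.

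Eligibility is the obstetrical provider's own judgement of whether the infant is non-vigorous. Several Appendix 2 admission criteria, such as lethargy, irritability and poor feeding, also call for judgement. Staff who believe one arm is doing worse could shift who is enrolled, who is admitted, or how well the assigned treatment is followed. The shift could differ between epochs at the same site, which is the contrast the crossover relies on.

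**Working it through.** No figure in the plan depends on this point, so the check is a comparison of passages with one count.

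**1. What the mailed findings refer to.** Two readings are possible. On the first, they are the results of the DSMB reviews, the subject of the paragraph. On the second, they are results after premature closure, the subject of the sentence just before. A recurring monthly mailing fits a one-time post-closure result poorly, and the sentence that follows returns to interim analysis. The first reading is the more natural, but the text does not settle it.

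**2. Does the mailing match the review schedule?** With the planned 1200 infants (Section V), the reviews fall at 200, 0.50 × 1200 = 600 and 0.75 × 1200 = 900 infants, which makes three reviews. Section III, Timeline, gives about 26 months of enrolment, hence up to about 26 monthly mailings. Most mailings could carry no new DSMB result, so the schedule does not show what they contain.

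**3. Section VIII against Section IX.** Section VIII sends findings to all staff as a standing monthly routine. Section IX has the analyses done apart from leadership and staff. Its one provision for sending a DSMB report to investigators is conditional on a change in known risk. A routine release to everyone and a conditional release to investigators cannot both be the rule for the same results.

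**4. What a monthly safety report could reveal.**

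| Form of the report | What a reader at one site learns |
|---|---|
| Own-site events only | Nothing new: the site already knows its events and its arm |
| Totals over all sites, with both arms contributing | No information by arm |
| Listed by site | Events by arm, for each site whose arm the reader knows |
| Listed by arm | Events by arm |

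The Monitoring paragraph allows any of these rows. The last two are the problem, and no passage excludes them.

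**5. Who knows which arm.** Section III documents that a site knows its own allocation. Knowledge of other sites' arms is plausible, because Section IV describes monthly teleconferences on how sites perform cord milking, but it is not stated.

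**The case against.** The strongest reply is that no leak by arm is described anywhere. The reviews are called blinded, and no passage provides for a table by arm or site. The Monitoring paragraph names no recipients, and Section IX mentions monthly adverse-event reports in a paragraph about what the DSMB receives, so the monthly report may be meant for the board. All of this is correct. A reader might infer that staff can see interim safety by arm; the documents do not establish that.

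The people at risk of influence are also partly shielded. Section VI says that those who assess infants at birth are neither co-investigators nor key personnel. Section IV asks that the intervention be left out of the infant's record. Appendix 2 fixes the reasons that count as admission. The reportable serious events are death, exchange transfusion, pulmonary hemorrhage and severe IVH, not NICU admission.

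These protections count, but they are partial. Section VI does not place the assessors outside the group receiving the mailing. The pediatric team attends high-risk deliveries, and Appendix 3 lists refusal by the neonatologist as a reason for not giving the assigned treatment, so the form allows for neonatologists knowing the arm.

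Finally, independence in Section IX can be read as governing who runs the analyses, not who receives results. That weakens one half of the conflict. The conditional release in Section IX remains. It is written for unanticipated events, yet it is hard to see why such reports would be released conditionally while routine findings went to all staff every month.

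**Conclusion.** The concern holds as a conflict between passages and an unguarded route for interim information. On its natural reading, Section VIII sends interim findings to staff of an open trial, contrary to the arrangement in Section IX. Neither the mailing nor the monthly safety report is limited to data that conceal the arm. It should be corrected.

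The conclusion rests on the mailed findings meaning DSMB review results. If only post-closure results were meant, the harm falls away for that sentence, but it still needs rewording and the Monitoring gap remains.

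The size of any bias cannot be derived from the documents. A reader might try: if staff admitted 5–15% more infants (relative) in an arm with a 25% rate, the rate would move by 0.25 × 5% = 1.25 to 0.25 × 15% = 3.75 points. That is 14–43% of the planned difference of 25 − 16.25 = 8.75 points. The 5–15% is purely assumed, and nothing in the plan links adverse-event counts to admission decisions. The result restates the assumption and should not be cited as an estimate. A reaction common to both arms would also largely cancel in the comparison.

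**What to change.** - **Section VIII, DSMB.** Replace the mailing sentence with text such as: *After each review, the DSMB sends the investigators its recommendation only. A report of a change in known risk is released as Section IX provides.* Keeping the second part preserves the existing safety release.
- **Section VIII, Monitoring.** Name the recipients. Limit reports sent to sites to that site's own enrolment, deviations and data queries. If serious adverse events are shown, give only totals pooled over all sites and arms, and only while sites in both arms contribute.
- **Closed reporting.** Keep cumulative adverse-event or outcome tables by site, epoch or arm for the DSMB and a data-center statistician who has no part in running the trial.
- **Section IX, SAE.** Leave the forwarding of single reports to the PI unchanged.
- **Consistency.** Reconcile both Section VIII paragraphs with Section IX.

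The cost is a few sentences and a monthly report split into open and closed versions. Sites would no longer see other sites' adverse-event counts, a small loss given that the DSMB continues to receive all of them.
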